12.3.11 Time-and-Motion (TAM) Studies

To assess clinic staff and patient time and resources required for visits specific to 1HP and 3HP initiation and follow-up, research staff will conduct time-andmotion (TAM) studies. TAM studies are designed to capture the amount of time needed to provide each unit of clinical and/or laboratory services to the patients. Sampling for TAM data collection will be stratified to ensure a broad coverage of visits by time of day, day of week, and time of year, plus inclusion of participants who require additional clinical evaluation (*e.g.*, for side effects) so that the data represents a range of clinical operational conditions in our study setting. The TAM data collection requires interaction with clinic staff; however, only minimal clinic staff involvement (shadowing/observation of staff) is needed, and these studies will not involve collection of protected health information (PHI). The TAM data collection will include a mix of directly observed (by study research staff) and self-reported data. All participating staff will provide informed consent. The TAM data will capture information on the amount of time spent conducting different TB procedures (*e.g.* assessing patient adherence) face-to-face with the patient, and other TB clinical tasks that are conducted without the presence of patients (e.g. administrative tasks such as review of medical charts).

13. SAFETY ASSESSMENT

13.1 Safety Assessment Overview

Responsibilities for ensuring the safety of study participants

National regulatory authorities, the sponsor, participating research institutions, Site Principal Investigator and clinical teams, and the study Principal Investigator share responsibility for ensuring that participants in this trial are exposed to the least possible risk of adverse events that may result from participation in this protocol.

The site principal investigator has a personal responsibility to closely monitor study participants and an inherent authority to take whatever measures necessary to ensure their safety. The principal investigator has the authority to terminate, suspend or require changes to the study for safety concerns. Site principal investigators determine severity and causality for each adverse event.

The protocol is approved by all local, national, and Sponsor-affiliated ethics committees. A referral network has been established for referring persons with adverse events to the hospital or local clinic.

13.2 Adverse Event Procedures and Reporting Requirements

13.2.1 Adverse Events

An adverse event is any untoward medical occurrence in a patient or clinical investigation subject administered a study agent and which does not necessarily have a causal relationship with the treatment received.

All Grade 2 or higher clinical or laboratory adverse events will be captured.

13.2.2 Study defined AEs

The study will capture study-defined adverse events including hypersensitivity syndrome, rash, peripheral neuropathy, hepatotoxicity, nausea and vomiting, and drug-related fever.

Participants will be trained to call the study team if they develop symptoms of hepatitis or rifamycin hypersensitivity syndrome, and the participant will have an unscheduled visit to evaluate as appropriate.

13.3.3 Serious Adverse Events

A serious adverse event (SAE) is defined as any untoward medical occurrence that

- results in death,
- is life-threatening,
- requires inpatient hospitalization or prolongation of existing hospitalization,
- results in persistent or significant disability/incapacity, or
- is a congenital anomaly/birth defect
- Other medically important conditions. This includes important medical events that may not be immediately life- threatening or result in death or hospitalization but may jeopardize the patient or may require intervention to prevent one of the outcomes listed in the definition above.

13.3.4 Adverse event (AE) reporting

Adverse events will be reported according to local and national regulatory requirements.

The purpose of AE reporting in this study is to ensure the safety of participants, and not to identify new AEs related to isoniazid or rifapentine. The 3HP regimen is approved by the US Food and Drug Administration (US FDA) and is recommended by WHO as TB preventive therapy. In this study, the use of 1HP in HIV-uninfected individuals is considered experimental. Investigators will monitor for adverse events in the study.

13.3.5 AEs requiring expedited reporting

The study will report all SAEs, including death from any cause, for any participant who had at least one dose of HP, as required by local and national regulatory agencies.

Any Grade 3 or higher hepatitis or hypersensitivity reaction; flu-like reaction,

or seizure will also be reported to the Principal Investigator, and Sponsor, and Johns Hopkins PI and study coordinator within 72 hours (three days) of site's knowledge.

Reporting a pregnancy will follow similar expedited reporting within 72 hours (three days of site's knowledge) to the Principal Investigator, and Sponsor, and Johns Hopkins PI and study coordinator.

13.3.6 AE Reporting period

The reporting period for AEs is from time of participant enrollment to the end of trial follow up for that participant. AEs occurring prior to exposure to the study agents in this trial do not require reporting.

13.3.7 Recording updated information on SAEs

Sites must follow each SAE until the SAE is resolved or stable if expected to remain chronic. Follow up should be according to clinical need, but not more than 45 days from the last visit.

Extra, annotated information and/or copies of test results may be provided separately.

13.3.8 Recurrent SAEs

If an SAE fully resolves but then re-occurs, the SAE is considered to be a new event.

13.3.9 Timeframe for SAE reporting

Clinical research sites must report all events that meet the regulatory agency definition of a SAE within 24 hours of awareness of the event. The event will be entered into the clinical database, and in addition, recorded on a SAE form and sent to the Johns Hopkins PI and central coordinator, and DMID via CROMS PVG.

SAEs will be submitted to all applicable ethical and regulatory agencies according to local and national requirements, or within 72 hours of the site becoming aware of the event.

13.3.10 Site investigator assessment and signature

A site physician investigator or sub-investigator must review and verify the completed SAE Form for accuracy and completeness and then sign the report. In the rare event that such physician(s) are not available for signature, sites may submit the SAE requiring reporting without the signature to meet reporting timeframe requirements. However, the completed SAE Form with

signature and any necessary corrections or additions must be submitted within 72 hours.

The site Principal Investigator (or designee) is responsible for designating at least one other physician at the site who can complete the form and provide signature to provide uninterrupted coverage of monitoring of SAEs.

Procedures

- 1. The site PI or designee evaluates the AE and determine whether it fulfils the criteria for seriousness.
- 2. If the SAE criteria is met, the SAE Form should be completed and signed by the responsible investigator.
- 3. The completed and signed SAE form should be submitted to regulatory authorities, and emailed to the Johns Hopkins PI and study coordinator.

14. CLINICAL MANAGEMENT

14.1 Clinical Management of Adverse Events

14.1.1 Toxicity grading tables

This study will grade toxicity and adverse events according to the *Division of AIDS (DAIDS) Table for Grading Adult and Pediatric Adverse Events, Corrected Version 2.1* (dated July 2017).

https://rsc.niaid.nih.gov/sites/default/files/daidsgradingcorrectedv21.pdf See Appendix V.

14.2 Toxicity management

14.2.1 Gastrointestinal

For nausea/vomiting and/or diarrhea \geq Grade 3 or for Grade 2 toxicity if symptoms were not present at the previous visit, all study drugs should be withheld until the symptoms have resolved. Reintroduce study drugs with caution. Antiemetic and antidiarrheal medication may be used at the site investigator's discretion. Labs should be checked as clinically indicated.

Every effort should be made to reintroduce the study drugs after symptoms improve or resolve.

14.2.2 Cutaneous

For Grade 2 or Grade 3 cutaneous events that occur after the first dose of HP, all study drugs should be withheld until the toxicity resolves. Study drugs should be reintroduced with caution.

Grade 4 cutaneous or mucocutaneous rash is a serious toxicity, and all study drugs should be permanently discontinued.

Study drugs may be discontinued at the discretion of the site investigator. Similarly, study drugs that are temporarily interrupted may be reintroduced at the discretion of the site investigator.

14.2.3 Rifamycin hypersensitivity syndrome (RHS)

Signs and symptoms of RHS may include hypotension, urticaria, angioedema, acute bronchospasm, conjunctivitis, thrombocytopenia, neutropenia or flu-like syndrome (weakness, fatigue, muscle pain, nausea, vomiting, headache, fever, chills, aches, rash, itching, sweats, dizziness, shortness of breath, chest pain, cough, syncope, palpitations). There have been reports of anaphylaxis

This syndrome has been associated with intermittent rifampin administration, and was reported in a rifapentine and isoniazid regimen study (Langdon 2004). In Study 26, flu-like and systemic drug reactions were reported by 3.5% of 3HP recipients compared to 0.4% of 9h recipients. More recently, among healthy volunteers receiving HP and dolutegravir, 2 of 4 volunteers experienced rifamycins hypersensitivity syndrome fever, hypotension, elevated transaminases), halting the study. (Brooks 2018) No hypersensitivity reactions were found with daily HP in the BRIEF TB study. We will carefully monitor participants for signs and symptoms of hypersensitivity reactions.

For participants who develop signs or symptoms of RHS:

- Hold study drug regimen
- Assess for RHS through clinical evaluation and laboratory testing, including comprehensive metabolic panel, CBC with differential, and other tests that are necessary to exclude likely alternative diagnoses. (e.g., should symptoms suggest influenza, a nasopharyngeal aspirate for viral testing could be sent).
- If Grade 3 or higher AE meets the definition for RHS (and symptoms are not clearly attributable to an alternative diagnosis), permanently discontinue the study drug regimen and notify the Core Team.

See Appendix III for a rifamycin hypersensitivity syndrome worksheet.

14.2.4 Drug-Associated Fever

If \geq Grade 3, all study drugs should be held until the participant is afebrile. Study drugs should be reintroduced with caution. If fever reoccurs on reintroduction, permanently discontinue study drugs.

14.2.5. Liver Toxicity

All study drugs will be stopped permanently if any of the following liver chemistry criteria are met:

- ALT \ge 3 × ULN and bilirubin \ge 2 × ULN (>35% direct bilirubin; bilirubin fractionation required)
 - NOTE: Serum bilirubin fractionation should be performed if testing is available. If testing is unavailable, record presence of detectable urinary bilirubin on dipstick, indicating direct bilirubin elevations and suggesting liver injury. If testing is unavailable and a subject meets the criterion of total bilirubin ≥2 × ULN, then the event meets liver stopping criteria;
- ALT ≥3 × ULN with symptoms or worsening of acute hepatitis or hypersensitivity such as fatigue, nausea, vomiting, right upper quadrant pain or tenderness, fever, rash, or eosinophilia, or
- ALT \geq 5 × ULN; regardless of symptoms

In the event of liver toxicity, appropriate evaluations for alternative causes may be pursued (viral hepatitis, alcohol exposure, etc.).

14.2.6 Peripheral Neuropathy

Peripheral neuropathy associated with INH is less common in HIV-uninfected individuals. Individuals who are at risk for developing peripheral neuropathy may be started on pyridoxine (vitamin B6) at the Investigator's discretion.

Participants with baseline peripheral neuropathy <Grade 2 according to the DAIDS Grading Table may be entered into the study, but should be monitored carefully for progression of the neuropathy.

For Grade 1 or 2, continue the study drugs and follow the participant more frequently for progression of peripheral neuropathy. Consider starting or increasing vitamin B6 dose.

For Grade 3 or 4, discontinue all study medication until toxicity resolves to Grade ≤ 2 . If peripheral neuropathy does not resolve despite discontinuation of study drugs, study drugs may be reintroduced at the site investigator's discretion.

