12.3 Other Study Procedures and Evaluations

12.3.1 Early Termination Visit

Participants who meet any one or more of the following criteria will be discontinued from study treatment:

• Pregnancy

• Any clinical adverse event, laboratory abnormality, intercurrent illness, other medical condition or situation occurs such that continued administration of study treatment is not in the best interest of the participant

• Participant request for premature discontinuation of study treatment A participant who is discontinued from study treatment should still remain on study, and continue with follow up visits as described in the schedule of evaluations.

A participant who withdraws consent will not continue to be followed.

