14.2.7 Other Toxicities

For toxicities that do not fall into one of the scenarios above, management will be as follows:

Grade 1 and 2: Participants may continue HP at the discretion of the site investigator with careful follow-up.

Grade 3 and 4: Study drugs should be held until symptoms have resolved (or until \leq Grade 2 or within normal limits). Study drugs may be permanently discontinued at the discretion of site investigator.

Site investigators are strongly encouraged to discuss discontinuations and reintroductions of study treatment with the core investigators to ensure consistency across sites.

If study drugs are suspended for any reason, participants in Arm A will have 8 weeks from enrollment to complete 28 doses of HP. Participants in Arm B will have 16 weeks from enrollment to complete at least 11 doses of HP. If the break in treatment is longer than 4 weeks, the participant will need to be rescreened for TB before recommencing HP.

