14.4 Criteria for Discontinuation of Study Medications

14.4.1 Criteria for Permanent Discontinuation

- Discontinuation for an Individual Participant
- Drug-related toxicity requiring tx discontinuation
- Pregnancy or breastfeeding. HP will be discontinued and the participant will be referred to routine care.
- Diagnosed with active TB disease
- Completion of study events
- Request by participant to terminate treatment
- Clinical reasons believed life threatening by the physician, even if not addressed in the toxicity section of the protocol
- Acquires HIV infection while on study

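### Protocol Section 14.2.6 lets study drugs be restarted in neuropathy that has not resolved, with no grade limit or cause condition

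*Protocol*

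**What the plan says.** Protocol Section 14.2.6 gives three instructions that bear on this point.

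- At low grade, dosing goes on: "For Grade 1 or 2, continue the study drugs and follow the participant more frequently for progression of peripheral neuropathy".
- At high grade, dosing stops: "For Grade 3 or 4, discontinue all study medication until toxicity resolves to Grade" 2 or lower.
- If the neuropathy persists off drug: "If peripheral neuropathy does not resolve despite discontinuation of study drugs, study drugs may be reintroduced at the site investigator's discretion".

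Section 14.2.7 adds time limits that apply whatever the reason for the suspension: "participants in Arm A will have 8 weeks from enrollment to complete 28 doses of HP", and "Participants in Arm B will have 16 weeks from enrollment to complete at least 11 doses of HP". A break of more than 4 weeks requires rescreening for TB before dosing resumes. The same section adds advice on consultation: "Site investigators are strongly encouraged to discuss discontinuations and reintroductions of study treatment with the core investigators".

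Two general stopping provisions also apply. Section 12.3.1 requires discontinuation when an event means that "continued administration of study treatment is not in the best interest of the participant". Section 14.4.1 lists "Drug-related toxicity requiring tx discontinuation" among the grounds for a permanent stop.

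The SAP adds no restart rule.

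**The concern.** The second and third instructions in Section 14.2.6 point in opposite directions for the same participant. Someone still at Grade 3 or 4 after a hold has not met the condition for ending it, yet failure to resolve is the circumstance in which the next sentence makes restart available. A site could resume isoniazid and rifapentine in a participant with ongoing Grade 3 or 4 neuropathy and, provided the investigator judged this acceptable, be within the text. Two sites could also handle the same case differently without either deviating.

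At stake are the safety of an individual participant and consistency between sites. Neuropathy is one of the targeted safety events in a trial whose rationale is uncertainty about the safety of 1HP in people without HIV, so the rule deserves to be unambiguous.

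**Working it through.** The plan states no figure on this point. The check is a reading of the rule against itself and its neighbours, followed by arithmetic on the time limits that the fix relies on.

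**1. When does the restart sentence add anything?**

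| Neuropathy after the hold | Already covered in 14.2.6? | Effect of the restart sentence |
|---|---|---|
| Fully resolved | Yes, the hold has ended | None; the sentence concerns non-resolution |
| Grade 1 or 2 | Yes, twice: the hold ends at Grade 2 or lower, and drugs continue at Grade 1 or 2 | None |
| Grade 3 or 4 | Yes, the hold continues | Permits restart |

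The sentence changes what a site may do only in the last row.

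**2. How do the neighbouring rules in Section 14.2 treat non-resolution?**

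- Gastrointestinal (14.2.1): held until symptoms resolve; reintroduction follows improvement or resolution.
- Cutaneous (14.2.2): Grades 2 and 3 are held until resolution; Grade 4 is a permanent stop. The investigator has discretion over reintroduction, but it is not triggered by non-resolution.
- Hypersensitivity (14.2.3): Grade 3 or higher is a permanent stop, with Core Team notification, unless another diagnosis clearly explains the symptoms.
- Fever (14.2.4): Grade 3 or higher is held until afebrile; recurrence on rechallenge is a permanent stop.
- Liver (14.2.5): fixed laboratory thresholds for a permanent stop.
- Other toxicities (14.2.7): Grades 3 and 4 are held until resolved, Grade 2 or lower, or normal; there is no restart provision for non-resolution.

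Only the neuropathy rule makes failure to resolve a route back to dosing.

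**3. Do the general provisions close the gap?** Sections 12.3.1 and 14.4.1 can stop treatment, but someone must first judge that continuing is against the participant's interest or that the toxicity requires discontinuation. Section 14.2.7 encourages discussion without making it a condition. None of the three sets a neuropathy grade or a cause requirement.

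**4. Is an outcome affected?** SAP Section 10.2.2 counts a participant with at least one targeted event of Grade 2 or higher. A Grade 3 or 4 neuropathy on treatment has already met that definition, so a later restart cannot change the participant's binary safety result.

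**5. How long a hold do the time limits allow?** Assume that no other doses are missed and the first dose is on day 0.

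- Arm A, 8 weeks = 56 days, 28 daily doses. Giving each dose a full day: 56 − 28 = 28 days. Counting only to the day of the last dose (day 27): 56 − 27 = 29 days.
- Arm B, 16 weeks = 112 days, 11 weekly doses. Giving each dose a full week: 112 − 77 = 35 days. Counting only to the day of the last dose (day 70): 112 − 70 = 42 days.

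Section 14.2.7 therefore supplies a usable limit of about 4 weeks of total hold in Arm A and 5 to 6 weeks in Arm B.

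**6. What could a permanent stop cost in the treatment-success outcome?** A participant stopped before 25 doses (Arm A) or 11 doses (Arm B) is unsuccessful. One participant is 1/250 = 0.4 percentage points in that arm.

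**The case against.** The strongest reply is that the sentence can be read more mildly. Section 14.2.7 lists symptom resolution and Grade 2 or lower as alternatives, so there 'resolved' means full resolution. On that usage, non-resolution in 14.2.6 could mean residual Grade 1 or 2 neuropathy, and the sentence would merely confirm that this does not bar restart. The wording is ambiguous to that extent. But the mild reading leaves the sentence with nothing to do, and 14.2.6 itself uses resolution to mean reaching Grade 2 or lower.

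A second reply is clinical. Persistence after the drugs are stopped is dechallenge information and may suggest another cause. That is a sensible reason for the sentence and probably its intent, but the text does not make it a condition.

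Third, the backstops are real. Once the criterion in Section 12.3.1 is judged to be met, discontinuation is mandatory, and discretion over restart also appears in 14.2.2. This stands, and it limits the point. A reader might infer that the protocol directs sites to dose through severe neuropathy or leaves participants unprotected. It does neither: restart is optional and remains subject to the best-interest test.

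Fourth, an amendment has a real approval burden for a rare event. This also stands and bears on timing.

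**Conclusion.** The point holds as a minor matter of participant safety. Taken literally, Section 14.2.6 releases its own Grade 2 threshold for a participant who remains at Grade 3 or 4, without a grade limit or a stated cause. The conclusion rests on reading the restart sentence as having some effect; if the authors meant only residual low-grade neuropathy, the defect is one of clarity and the same rewording cures it.

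The size cannot be quantified. Protocol Section 11.1.2 puts isoniazid peripheral neurotoxicity below 0.2% at conventional doses, and a reader might infer a bound of fewer than 500 × 0.002 = 1 case in the trial. The documents do not support that as a bound. The figure states no grade, covers isoniazid toxicity whereas the rule covers neuropathy of any cause, and is described as dose dependent, while Arm B takes 900 mg weekly against a usual daily maximum of 300 mg. The documents give no rate for unresolved Grade 3 or 4 neuropathy, nor for restart. Rare is as far as they go.

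A reader might also infer bias in the primary safety comparison. That does not follow, because the qualifying event has already been counted. No outcome definition, SAP analysis or power figure is affected.

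**What to change.** Replace the last sentence of Protocol Section 14.2.6 with: *Study drugs may not be reintroduced while neuropathy remains Grade 3 or 4 unless a non-drug cause is documented and the Core Team is notified; otherwise, if it has not resolved to Grade ≤2 in time to complete dosing within the 14.2.7 limits (8 weeks Arm A, 16 weeks Arm B), permanently discontinue study drugs.*

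The cause exception and the notification follow the pattern already used for hypersensitivity in 14.2.3, so the dechallenge reasoning is kept but has to be recorded.

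The amendment should name the 14.2.7 limits explicitly, because Protocol Section 12.1.5 and SAP Section 10.2.1 define completion within 6 weeks (1HP) and 18 weeks (3HP). Under a 6-week limit, the Arm A hold would shrink to 42 − 28 = 14 days. The 8- and 16-week limits match the periods in the primary outcome definition in Protocol Section 15.2.1.

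The cost is one sentence and a note to the two sites, with no change to the SAP, visits or sample size. Sections 18.1 and 18.15 require approval of modifications and name the local committees in Rio de Janeiro and Manaus, the national commission and the Johns Hopkins IRB. The change is therefore best carried in the next amendment rather than made alone. Sites lose a little discretion, and a participant stopped early may count as unsuccessful.
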